8.1.3. Treatment and Disposition of Subjects

Subject evaluation groups will show end of study subject disposition and will show which subjects were analyzed for pharmacokinetics, immunogenicity, ^{CCI} as well as for safety (adverse events and laboratory data). Frequency counts will be supplied for subject discontinuation(s) by treatment.

Data will be presented by study part (SAD/MAD, Nasal Polyps and Atopic Dermatitis) and cumulatively across all study parts. Data will be reported in accordance with the sponsor reporting standards.

8.1.4. Demographic and Clinical Examination Data

A breakdown of demographic data will be provided for age, race, weight, body mass index and height. Each will be summarized by sex at birth and 'All Subjects' for each cohort separately and overall in accordance with the sponsor reporting standards. Data will be presented by study part (SAD/MAD, Nasal Polyps and Atopic Dermatitis) and cumulatively across all study parts.

8.1.5. Discontinuation(s)

Subject discontinuations, temporary discontinuations or dose reductions due to adverse events will be detailed and summarized by treatment. Data will be presented by study part (SAD/MAD, Nasal Polyps and Atopic Dermatitis) and cumulatively across all study parts.

Data will be reported in accordance with the sponsor reporting standards.

8.1.6. Adverse Events

Data will be presented by study part (SAD/MAD, Nasal Polyps and Atopic Dermatitis) and cumulatively across all study parts. Adverse events will be reported in accordance with the sponsor reporting standards.

8.1.7. Laboratory Data

Laboratory data will be listed and summarized by treatment in accordance with the sponsor reporting standards. Baseline is as defined in Section 6.2.2.

8.1.8. Vital Signs Data

Absolute values and changes from baseline in supine systolic and diastolic blood pressure and pulse rate will be summarized by study part (SAD/MAD, Nasal Polyps, Atopic Dermatitis). They will be further summarized by cohort, treatment and time postdose, according to sponsor reporting standards as appropriate. Tables will be paged by parameter. Baseline is as defined in Section 6.2.3.

Mean changes from baseline for supine systolic and diastolic blood pressure and pulse rate will be plotted against time postdose. On each plot there will be 1 line for each cohort. Data from all cohorts will be plotted on the same figure using separate lines for the 2 placebos. Corresponding individual plots of changes from baseline will also be produced for each cohort and treatment.

For supine systolic and diastolic blood pressure and pulse rate, the differences between each dose and placebo (dose – placebo) will be summarized (N, mean, 90% confidence interval) and plotted (mean) for each cohort, dose and timepoint (including baseline).

Maximum absolute values and changes from baseline for vital signs will also be summarized descriptively by treatment using categories as defined in Appendix 1. Numbers and percentages of subjects meeting the categorical criteria will be provided. All planned and unplanned postdose timepoints will be counted in these categorical summaries. All values meeting the criteria of potential clinical concern will be listed.

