2.2. Endpoints

2.2.1. Primary Endpoints

Parts 1 and 2

• Incidence, severity and causal relationship of treatment emergent adverse events (TEAEs) and withdrawals due to TEAEs through the end of the study.

- Incidence and causal relationship of treatment emergent serious adverse events (SAEs) through the end of the study.
- Incidence and magnitude of abnormal chemistry, hematology, and urinalysis laboratory findings through the end of the study.
- Abnormal and clinically relevant changes in vital sign parameters through the end of the study.
- Abnormal and clinically relevant changes in electrocardiogram (ECG) parameters through the end of the study.

- Incidence, severity and causal relationship of treatment emergent adverse events (TEAEs) and withdrawals due to TEAEs through the end of the study.
- Incidence and causal relationship of treatment emergent serious adverse events (SAEs) through the end of the study.
- Incidence and magnitude of abnormal chemistry, hematology, and urinalysis laboratory findings through the end of the study.
- Abnormal and clinically relevant changes in vital sign parameters through the end of the study.
- Abnormal and clinically relevant changes in electrocardiogram (ECG) parameters through the end of the study.

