- 8. Part 1 and Part 2: Pregnant female subjects, breastfeeding female subjects, male subjects with partners currently pregnant, or male or female subjects pursuing artificial reproductive technologies including but not limited to sperm/egg donation.
 - Part 1: Female subjects of childbearing potential, male subjects able to father children who are unwilling or unable to use a highly effective method of contraception as outlined in this protocol for the duration of the study (see Section 4.3.1.5, Lifestyle Guidelines).
 - Part 2: Female subjects of childbearing potential unless they have a documented bilateral tubal ligation or bilateral salpingectomy, male subjects able to father children who are unwilling or unable to use a highly effective method of contraception as outlined in this protocol for the duration of the study (see Section 4.3.1.5, Lifestyle Guidelines).
- 9. A positive urine drug screen (see Section 7.1.1.1).
- 10. History of regular alcohol consumption exceeding 7 drinks/week for females or 14 drinks/week for males; (1 drink = 5 ounces of wine or 12 ounces of beer or 1.5 ounces of hard liquor) within 6 months of Screening.
- 11. **Part 1**: Screening supine blood pressure ≥140 mm Hg (systolic) or ≥90 mm Hg (diastolic), following at least 5 minutes of supine rest. If blood pressure (BP) is ≥140 mm Hg (systolic) or ≥90 mm Hg (diastolic), the BP should be repeated two more times and the average of the three BP values should be used to determine the subject's eligibility.

- **Part 2:** Screening supine blood pressure ≥ 160 mm Hg (systolic) or ≥ 100 mm Hg (diastolic), following at least 5 minutes of supine rest. If blood pressure (BP) is ≥ 160 mm Hg (systolic) or ≥ 100 mm Hg (diastolic), the BP should be repeated two more times and the average of the three BP values should be used to determine the subject's eligibility.
- 12. Screening supine 12-lead ECG demonstrating QTc >450 msec or a QRS interval >120 msec. If QTc exceeds 450 msec, or QRS exceeds 120 msec, the ECG should be repeated two more times and the average of the three QTc or QRS values should be used to determine the subject's eligibility.

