- 20. Screening supine blood pressure ≥160 mm Hg (systolic) or ≥100 mm Hg (diastolic), following at least 5 minutes of supine rest. If blood pressure (BP) is ≥160 mm Hg (systolic) or ≥100 mm Hg (diastolic), the BP should be repeated two more times and the average of the three BP values should be used to determine the subject's eligibility.
- 21. Screening supine 12-lead ECG demonstrating corrected QT (QTc) >450 msec or a QRS interval >120 msec. If QTc exceeds 450 msec, or QRS exceeds 120 msec, the ECG should be repeated two more times and the average of the three QTc or QRS values should be used to determine the subject's eligibility.
- 22. Blood donation (excluding plasma donations) of approximately 1 pint (500 mL) or more within 56 days prior to dosing.
- 23. Treatment with an investigational drug within 28 days (or as determined by the local requirement) or 5 half-lives preceding the first dose of study treatment (whichever is longer).
 - Any investigational or experimental therapy taken or procedure performed for AD, psoriasis, psoriatic arthritis or rheumatoid arthritis in the previous 1 year should be discussed with the Pfizer Medical Monitor (or designee). Subjects cannot participate in studies of other investigational or experimental therapies or procedures at any time during their participation in this study.
- 24. Have received any of the following treatment regiments with the specified timeframes outlined below:
 - Systemic Corticosteroids:
 - Subjects receiving systemic corticosteroids within 4 weeks prior to first dose of study drug or scheduled to receive systemic corticosteroids during the study period for another condition. Subjects receiving doses of depot preparations of parenteral corticosteroids within 6 weeks of the predicted end of release of the corticosteroid from the depot are excluded. See Exclusion Criteria 28 for additional asthma exacerbation corticosteroid restrictions.
 - Leukotriene antagonists/modifiers:
 - Asthmatic subjects taking stable doses of leukotriene antagonists/modifiers for at least 28 days prior to first dose of study drug may be included.

- Any prior or current use of Anti-IL-33 targeted therapies is exclusionary.
- Within 6 months of first dose of study drug:
 - Anti-IL-4 and/or IL-13 targeted therapies (eg, lebrkizumab, tralokinumab) except for dupilumab (within 4 months of first dose of study drug).
 - mepolizumab, reslizumab.
- Within 12 months of first dose of study drug:
 - Benralizumab.

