Appendix 1. Categorical Classes for ECG and Vital Signs of Potential Clinical Concern

Categories for QTcF

QTcF (ms)	450≤ max. <480	480≤ max.<500	max. ≥500
QTcF (ms)	$30 \le \max. \le 60$	max. ≥60	
increase from			
baseline			

[figure not shown]
Categories for PR and QRS

PR (ms)	max. ≥300	
PR (ms) increase	Baseline >200	Baseline ≤200 and
from baseline	and max.	max. ≥50%
	\geq 25% increase	increase
QRS (ms)	max. ≥140	
QRS (ms)	≥50% increase	
increase from		
baseline		

Categories for Vital Signs

Systolic BP (mm Hg)	min. <90	
Systolic BP (mm Hg)	max. decrease ≥30	max. increase ≥ 30
change from baseline		
Diastolic BP (mm Hg)	min. <50	
Diastolic BP (mm Hg)	max. decrease ≥20	max. increase ≥ 20
change from baseline		
Supine pulse rate (bpm)	min. <40	max. >120
Standing pulse rate (bpm)	min. <40	max. >140

Measurements that fulfill these criteria are to be listed in report.

[figure not shown]
CCI			
-			

CCI		
	-	

CCI

[figure not shown]
CCI		

CCI			
CCI			
CCI			

[figure not shown]

CCI

CCI	

CCI						
			I		I	

CCI		

CCI	

CCI

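### Appendix 1 has no upper category for absolute blood pressure, so a high reading reached by a rise below 30 systolic and 20 diastolic is not counted or listed as a value of potential clinical concern

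*SAP*

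**What the plan says.** Protocol 2.2.1 makes this a primary safety endpoint in every part: "Abnormal and clinically relevant changes in vital sign parameters through the end of the study". Protocol 9.6 adds that vital sign abnormalities of potential clinical concern will be described.

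SAP 8.1.8 puts this into practice through categories: "Maximum absolute values and changes from baseline for vital signs will also be summarized descriptively by treatment using categories as defined in Appendix 1". Subject counts with percentages are promised, over planned and unplanned postdose timepoints, and "All values meeting the criteria of potential clinical concern will be listed".

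The categories are in SAP Appendix 1, under "Categories for Vital Signs". For blood pressure the rows are:

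- absolute systolic: minimum below 90 mm Hg, nothing else;
- absolute diastolic: minimum below 50 mm Hg, nothing else;
- systolic change: a decrease of 30 or more, or "max. increase ≥ 30";
- diastolic change: a decrease of 20 or more, or "max. increase ≥ 20".

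Outside the categories, SAP 8.1.8 also summarises absolute blood pressure and its change by part, cohort, treatment and time. It plots mean and individual changes and gives differences from placebo with 90% confidence intervals.

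**The concern.** The text of 8.1.8 speaks of maximum absolute values, but the table it points to has no row in which a maximum blood pressure could be placed. Absolute blood pressure is the exception in Appendix 1: supine pulse has an upper limit (above 120 bpm), and so do QTcF (top class 500 ms and over), PR (300 ms and over) and QRS (140 ms and over).

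Appendix 1 is the only rule stated in the SAP for flagging an individual blood pressure value. Followed exactly, it gives a two-sided account of changes and a one-sided account of levels. A subject who starts high and rises moderately produces no count and no listed value. Such subjects are most likely in Parts 2 and 3, which admit higher entry pressures than Part 1.

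**Working it through.** The plan states no figure to reproduce here. The check is to apply the Appendix 1 criteria as written and find the highest postdose reading that meets none of them.

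**Inputs**

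- Rise criteria from SAP Appendix 1: 30 or more systolic, 20 or more diastolic.
- Low criteria from SAP Appendix 1: below 90 systolic, below 50 diastolic, or a fall of 30 or 20. None applies to a rising pressure at these levels.
- Part 1 entry, Protocol 4.1.2 criterion 11: "Screening supine blood pressure ≥140 mm Hg (systolic) or ≥90 mm Hg (diastolic") is excluded, so the highest eligible value is 139/89.
- Part 3 entry, Protocol 4.1.2.1 criterion 20: "Screening supine blood pressure ≥160 mm Hg (systolic) or ≥100 mm Hg (diastolic") is excluded, so the highest eligible value is 159/99. Part 2 uses the same limits (Protocol 4.1.2 criterion 11).
- Baseline is the last Day 1 pre-dose value (SAP 6.2.3). Assumption: it equals the screening value.

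**Highest unflagged reading.** In whole mm Hg, a rising reading goes unflagged when the systolic rise is at most 29 and the diastolic rise at most 19. The highest unflagged reading is therefore baseline + 29 over baseline + 19.

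| Part | Baseline | Systolic | Diastolic | Highest unflagged |
|---|---|---|---|---|
| 1 | 139/89 | 139 + 29 = 168 | 89 + 19 = 108 | 168/108 |
| 2 and 3 | 159/99 | 159 + 29 = 188 | 99 + 19 = 118 | 188/118 |

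**Lowest baseline from which a given level can be reached unflagged** (level minus 29 or 19):

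- systolic 140: 140 − 29 = 111; systolic 160: 160 − 29 = 131;
- diastolic 90: 90 − 19 = 71; diastolic 100: 100 − 19 = 81.

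The gap is therefore not confined to subjects at the eligibility ceiling.

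**Two ordinary cases**

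- 120/75 to 165/96: rises of 45 and 21. Both rise criteria are met, so the subject is counted and the values listed.
- 145/85 to 165/102: rises of 20 and 17. No criterion is met, so there is no count and no listing, although the final reading is higher on diastolic and equal on systolic.

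**Do the other outputs fill the gap?** The by-time summaries of absolute pressure contain these readings, but they do not give the number or percentage of subjects reaching a high level. The individual plots show changes, not levels. The sentence bringing in unplanned timepoints refers to the categorical summaries, so an unscheduled high reading is assured a place only in the table that has no row for it.

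**The case against.** The strongest reply is that the primary endpoint is worded as changes, and the change categories are two-sided, counted over all timepoints and listed. High values also remain visible in the by-time absolute summaries; Protocol 9.6 provides for ongoing safety review; and Protocol 8.5 makes an abnormal finding an adverse event if it is symptomatic, needs work-up or treatment, or is judged to be one. Groups are small (6 active and 2 placebo per Part 1 cohort, 28 subjects in Part 3), and no hypothesis is tested. All of this stands. It limits the consequence, but none of it produces a count of subjects with high readings.

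Two stronger readings are tempting, and the documents do not support either.

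- A reader might infer that hypertensive readings go uncounted altogether. They do not: any reading reached by a rise of at least 30 systolic or 20 diastolic is counted and listed, as a rise.
- A reader might take 140/90 and 160/100 as postdose limits that the SAP fails to apply. They are screening exclusions, judged on the average of three readings when the first is raised. The documents state no postdose limit for high blood pressure.

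Two uncertainties remain. The sponsor reporting standards cited in 8.1.8 are not available and might add displays. A cell of the Appendix 1 table could also have been lost. However, the absolute PR and QRS rows likewise have an empty second cell, so the blanks look genuine.

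**Conclusion.** The point holds in a narrow form. SAP 8.1.8 announces a count of maximum absolute values that Appendix 1 cannot supply for blood pressure. What is missed is a high reading reached by a rise of at most 29 systolic and 19 diastolic.

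The 188/118 and 168/108 figures illustrate the width of the gap. They are not expected cases: they need a subject at the eligibility limit on both pressures, and they assume that the Day 1 baseline equals screening. Nor are they a strict ceiling, because the blood pressure exclusion applies at screening and the Day 1 value may be higher. The documents give no baseline blood pressure distribution, so the number of subjects affected cannot be estimated.

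No test, error rate or sample size is involved. The consequence is an incomplete tabulation for a primary safety endpoint, which is worth correcting because the correction is cheap.

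**What to change.** Add upper absolute categories for systolic and diastolic pressure to Appendix 1, with the sponsor stating the rationale for the limits. The protocol's screening limits (140/90 in Part 1, 160/100 in Parts 2 and 3) are an available default. One common limit, such as 160/100, would suit the combined safety summaries planned in SAP 8.1 better than part-specific limits.

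Count subjects reaching the limit postdose, by treatment within part. Show separately those below and those at or above the limit at baseline: restricting the count to the first group would drop part of the raised-baseline group that the present categories miss. List the values.

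Rewording 8.1.8 so that blood pressure is described as minimum values and changes would remove the mismatch, but would leave the gap.

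The cost is a few table rows and a sentence of SAP text, on data already collected. The small downside is that isolated high readings will be counted in both arms, and a limit of 140 in Part 1 would count a move from 139 to 140. The counts should therefore be read next to placebo. Removing the standing pulse row, which has no use when the planned measurements are supine, is tidying only and changes no result.

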8.1.9. ECG Data

Absolute values and changes from baseline in QT, heart rate, QTcF, PR and QRS will be summarized by study part (SAD/MAD, Nasal Polyps, Atopic Dermatitis). They will be further summarized by cohort, treatment and time postdose using sponsor reporting standards as appropriate. Tables will be paged by parameter. Baseline is as defined in Section 6.2.4. All triplicate measures will be averaged prior to summarization. Telemetry data will not be summarized along with other ECG data but listed in adverse events as appropriate.

Mean changes from baseline in QT, heart rate and QTcF will be plotted against time postdose. On each plot there will be 1 line for each treatment. Data from all cohorts will be plotted on the same figure using separate lines for the 2 placebos. Corresponding individual plots of changes from baseline will also be produced for each cohort and treatment.

Changes from baseline in QTcF will also be plotted separately against drug concentrations. This will be a scatter plot for all observations where QTcF and drug concentration are recorded. Placebo data will also be included (with drug concentration set to zero). Different symbols will be used for each cohort. There will be 1 plot for each of the parts of the study (Part 1, 2, 3), for Part 1 the SAD and MAD data will be plotted separately. Maximum increase from baseline (0 to 12 hours) for QTcF, heart rate, QT, PR and QRS will be summarized by cohort and treatment, according to sponsor reporting standards for the first two parts (SAD/MAD and Nasal Polyps) of the study.

In addition for QTcF, heart rate and QT, and change from baseline for each subject will be summarized and plotted (N, mean, 90% confidence interval) for each cohort, dose and timepoint (including baseline).

ECG endpoints and changes from baseline (QTcF, PR and QRS) will also be summarized descriptively by cohort and treatment using categories as defined in Appendix 1 (for QTc these correspond to ICH E141).¹ Numbers and percentages of subjects meeting the categorical criteria will be provided. All planned and unplanned postdose timepoints will be counted in these categorical summaries. All values meeting the criteria of potential clinical concern will be listed.

Listings of subjects with any single postdose value \geq 500 msec will also be produced for QTcF.

QTcB will be listed only and not summarized.

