1.2.3. Nonclinical Pharmacokinetics

After a single intravenous (IV) dose of PF-06817024 to cynomolgus monkeys, the mean clearance (CL), volume of distribution at steady state (V_{ss}), and terminal half-life ($t_{1/2}$) values were 0.058 mL/h/kg, 56 mL/kg, and approximately 18 days, respectively. Additionally, single dose toxicokinetics (TK) were evaluated after IV or subcutaneous (SC) dosing in an exploratory toxicity study. Systemic exposure increased with increasing dose in the IV dose groups and sex-related differences in exposure were not observed. SC bioavailability was approximately 78%. No anti-drug antibodies (ADA) were detected following a single IV dose to cynomolgus monkeys.

After repeat IV or SC administration of PF-06817024 to cynomolgus monkeys in 13- and 27-week toxicity studies, systemic exposure (as assessed by the highest drug concentration observed in serum [C_{max}] and area under the serum drug concentration-time curve from 0 to 504 hours [AUC₅₀₄]) increased with increasing dose in the IV dose groups. Accumulation was observed with mean Area under the C_{urve} (AUC) ratios ranging from 1.4 to 3.2 between Day 1 and Day 64 or 169. There were no apparent sex-related differences in systemic exposure observed. The incidence of antidrug antibody (ADA) induction to PF-06817024 was 42% across all-repeat dose groups in the 13-week study and 33% in the 27 week study. Exposures (as assessed by maximum observed concentration (C_{max}) and AUC₅₀₄) were generally similar in ADA-positive animals compared to ADA-negative animals.

Based on the pharmacokinetics (PK) observed in cynomolgus monkeys, the PK of PF-06817024 in humans is predicted based on allometric scaling and the PK of PF-06817024 in humans is assumed to be linear. The projected PK parameters include absorption rate constant of 0.18 day⁻¹, SC bioavailability of 78%, plasma CL of 0.082 L/day, inter-compartmental CL of 0.39 L/day, V_{ss} of 2.1 L (central) and 2.4 L (peripheral), and a $t_{1/2}$ of 41 days.

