1.2.5.2. PK Data

Based on a preliminary, draft dataset obtained in January 2018 and including interim data from subjects in the first two parts of the study, a non-compartmental PK analysis was performed and the derived PF-06817024 PK parameters are summarized descriptively in Table 1.

Following single IV doses in healthy subjects, the median time for occurrence of maximal concentration (T_{max}) ranged between 1.76 and 3 hours, while the median T_{max} after SC administration (30 mg) was 338 hours (\approx 14 days). PF-06817024 had a prolonged half-life ($t_{1/2}$) with mean values ranging from 79 to 94 days across all single dose healthy volunteer cohorts. Both maximal plasma concentration (C_{max}) and area under the concentration-time curve from time 0 to infinity (AUC $_{inf}$) appeared to be approximately dose proportional in healthy subjects across the 10-1000 mg IV range (see Table 1), indicating that PF-06817024 exhibits linear kinetics in humans within this dose range. Clearance (CL) values (geometric mean) ranged from 0.00206 L/h to 0.00259 L/h across all single IV dose healthy volunteer cohorts. Using the calculated geometric means of AUC $_{inf}$ after single IV infusion and SC administration of the same dose (30 mg) in healthy subjects (8579/14590, see Table 1), the bioavailability (F) after SC administration is approximately 59% relative to IV infusion.

Multiple dose PK data were available only for 4 healthy subjects from the 100 mg IV cohort who received an additional 100 mg IV dose. The (geometric) mean C_{max} after the second dose was 42.47 µg/mL (geometric CV of 11%) across these 4 subjects and the associated median T_{max} was 1.54 hours. The (geometric) mean area under the concentration-time curve from the time of the second dose until 720 hours post-dose (AUC_{τ}) and until infinity (AUC_{inf}) was 16540 (geometric CV of 13%) and 73400 µg•hr/mL (geometric CV of 23%) respectively. Finally, the mean calculated $t_{1/2}$ after the second dose was 108 days (standard deviation (SD) of 10).

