9.6.1. Electrocardiogram (ECG) Analysis

Abnormal and clinical relevant changes for the ECG parameters QT interval, heart rate, QTc interval, PR interval and QRS interval will be summarized by treatment and time.

The number (%) of subjects with maximum post dose QTc values and maximum increases from baseline in the following categories will be tabulated by treatment:

Safety QTc

	Borderline (msec)	Prolonged (msec)
Absolute Value	≥450 - <480	≥480
Absolute Change	30-<60	≥60

In addition, the number of subjects with corrected and uncorrected QT values ≥500 msec will be summarized.

If more than one ECG is collected at a nominal time post dose (for example, triplicate ECGs), the mean of the replicate measurements will be used to represent a single observation at that time point. If any of the three individual ECG tracings has a QTc value \geq 500 msec, but the mean of the triplicates is not \geq 500 msec, the data from the subject's individual tracing will be described in a safety section of the study report in order to place the \geq 500 msec value in appropriate clinical context. However, values from individual tracings within triplicate measurements that are \geq 500 msec will not be included in the categorical analysis unless the average from the triplicate measurements is also \geq 500 msec. Changes from baseline will be defined as the change between QTc post dose from the time-matched average baseline triplicates on Day 0, or the average of the pre-dose triplicate values on Day 1.

Part 3 ECG data analysis will be done as described above.

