Figure 1 demonstrates the study design with the select SAD cohorts rolling over into the multiple dose component. Depending on the safety, ^{CCI} and pharmacokinetic data available, dose escalation may be adjusted to doses other than those planned in the study. Intermediate doses can be evaluated instead of or in addition to the planned dose levels. A possible dosing scenario is included in the schematic.

• Cohort 1 (n=8): 10 mg active (n=6) or placebo (n=2), IV.

- Cohort 2 (n=8): 30 mg active (n=6) or placebo (n=2), IV.
- Cohort 3 (n=8): 100 mg active (n=6) or placebo (n=2), IV x 2 doses. [n=4 in MAD cohort].
- Cohort 4 (n=8): 300 mg active (n=6) or placebo (n=2), IV x 2 doses. [no MAD].
- Cohort 5 (n=8): 1000 mg active (n=6) or placebo (n=2), IV x 2 doses. [no MAD].
- *Cohort 6 (n=8): 2000 mg active (n=6) or placebo (n=2), IV.* [dose escalation stopped before 2000 mg dose group].
- Cohort 7 (n=8): 100 mg (first dose) followed by 300 mg (second dose) active (n=6) or placebo (n=2), SC. [Second dose not given, 100 mg dose changed to 30 mg].

2.2. Part 2:

One or more cohorts of CRSwNP patients will receive a single dose of PF-06817024. Randomization will occur after safety data from Day 8 and PK data through at least Day 5 of the same or higher dose in Part 1 of the study has been reviewed and deemed safe.

• Cohorts 8 and 9: Subjects in each cohort will be randomized in either a 1:1 or 2:1 (PF-06817024: placebo) ratio, depending on the number of cohorts and the emerging data. Up to approximately 10 active (per dose) and approximately 15 placebo (overall) subjects will be enrolled in Part 2 for a planned total of up to approximately 35 subjects.

2.3. Part 3

- Part 3 will consist of a single cohort of subjects with moderate to severe AD
- Cohort 13: Approximately 20 subjects in this cohort will be randomized to receive PF-06817024 or placebo in a 3:1 ratio (PF-06817024: placebo). Additional subjects up to a total of approximately 32 [28 actually enrolled] may be enrolled in a 3: 1 ratio (PF-06817024: placebo) CCI Subjects in this cohort randomized to PF-06817024 will receive a planned dosing regimen consisting of a 600 mg IV loading dose followed by 3 doses of 300 mg IV every 4 weeks.

Note that subjects were randomized 2:1 by site under protocol amendment 4 and then randomized centrally in a 3:1 ratio under amendment 5.

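### The 0–12 h ECG maximum-increase table closes well before subcutaneous exposure peaks, so its Cohort 7 rows need a longer period and a footnote

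*SAP*

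**What the plan says.** SAP 8.1.9 states: "Maximum increase from baseline (0 to 12 hours) for QTcF, heart rate, QT, PR and QRS will be summarized by cohort and treatment". It applies this "for the first two parts (SAD/MAD and Nasal Polyps) of the study" and makes no separate provision for SC dosing. Cohort 7, the only SC cohort, belongs to Part 1. The SAP's design section records what happened to it: "Second dose not given, 100 mg dose changed to 30 mg". The planned size was 6 active and 2 placebo.

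On timing, Protocol 1.2.5.2 reports that the median Tmax after single IV doses in healthy subjects "ranged between 1.76 and 3 hours", while the median "after SC administration (30 mg) was 338 hours". Protocol Table 1 gives an SC range of 338 to 1080 h in 6 subjects.

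The same SAP section plans several ECG outputs with no 12-hour limit:
- values and changes for all five parameters by cohort, treatment and time since dosing;
- mean and individual change plots;
- a scatter of QTcF change against concentration;
- category counts for QTcF, PR and QRS that include every post-dose reading, scheduled or not.

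Protocol 9.6.1 says that subjects with "maximum post dose QTc values and maximum increases from baseline in the following categories will be tabulated by treatment". That also carries no 12-hour limit.

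**The concern.** A 12-hour window suits an infusion, because the IV median Tmax falls inside it. For a slowly absorbed SC antibody it covers only the start of the rise. Placed in one table by cohort, the SC row would sit beside IV rows as if it described the same thing, the largest ECG change around peak exposure. It would describe the period before most of the exposure arrives, and a small maximum there would say little about the drug.

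The other outputs cover this better for some parameters than for others. The all-time categories take in QTcF, PR and QRS only. For ECG heart rate and uncorrected QT, the 0–12 h table is the only place where the SAP summarizes each subject's maximum increase. The by-time means and individual plots do not replace a per-subject maximum.

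**Working it through.** **1. Which ECGs fall in the window.** Schedule of Activities Table A lists Part 1 post-dose ECGs at 1, 2, 8, 12, 24, 48, 72 and 96 h. Table B adds Days 32, 61, 91, 121, 151, 181 and 211. That is 8 + 7 = 15 scheduled readings, of which 4 lie within 0–12 h. None is listed at Day 8 or Day 15. The earliest observed SC Tmax (338 h) is 338 − 12 = 326 h after the window closes, and 12/338 = 3.6% of the time to the median peak.

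**2. Reproduce the plan's own SC projection.** Inputs from Protocol 1.2.3: "SC bioavailability of 78%, plasma CL of 0.082 L/day", with ka 0.18/day, inter-compartmental clearance 0.39 L/day, and volumes 2.1 and 2.4 L. The model is two-compartment with first-order absorption, solved numerically for 100 mg SC.
- AUCinf = F × Dose/CL = 0.78 × 100/0.082 × 24 = 22,829 µg·h/mL (Protocol Table 2: 22,813).
- Cmax = 14.57 µg/mL (Table 2: 14.5).
- Cav over 720 h = 12.05 µg/mL (Table 2: 12.0).

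All three agree within 1%, so this is the plan's model. It puts the peak at 188.5 h, and concentration at 1.9% of peak at 1 h, 14.3% at 8 h and **20.8% at 12 h**.

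**3. Estimate from observed SC data.** Inputs from Protocol Table 1, 30 mg SC: Tmax 338 h = 14.08 days, half-life 93.58 days (SD 13.82), Cmax 2.471 µg/mL. One-compartment first-order absorption is assumed.
- ke = ln 2/93.58 = 0.00741/day.
- Solving ln(ka/ke)/(ka − ke) = 14.08 gives ka = 0.260/day.
- C(t) is proportional to exp(−ke·t) − exp(−ka·t). At 12 h (0.5 day): 0.9963 − 0.8781 = 0.1182. At the peak: 0.9009 − 0.0257 = 0.8752.
- Ratio = 0.1182/0.8752 = **13.5%**, that is 0.135 × 2.471 = 0.33 µg/mL.
- At 1 h the ratio is 1.2%. The window holds about 0.02% of total SC AUC.

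**4. Range.** Half-life ± 1 SD gives 13.1–13.9% at 12 h. Tmax at the upper extreme of 1080 h gives 3.4%. As a cross-check, the two-compartment model with observed 30 mg IV clearance (0.002055 × 24 = 0.0493 L/day) and ka of 0.10 or 0.15/day gives Tmax of 449.5 or 267.5 h, which brackets 338 h. Concentration at 12 h is then 13.0% or 17.4% of peak.

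**5. What later ECGs add.** Under the models of steps 3 and 2 respectively, 96 h is at 71% or 89% of peak and Day 32 (744 h) at 91% or 68%.

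**The case against.** The strongest reply is that nothing is hidden or lost. A reader might infer that late SC ECGs drop out of the analysis. They do not: by-time summaries, individual plots, the concentration scatter and the all-time categories all use them, and QTcF values of 500 msec or more are listed. A reader might also infer a conflict with Protocol 9.6.1. The unrestricted maximum there is the QTc category table, which the SAP also leaves unrestricted; the 0–12 h table is an additional descriptive output. Nor are the differing periods concealed, since SAP 8.1.9 labels each one. All of this stands.

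The scale is also small. One cohort is affected, and its Cmax (2.471 µg/mL) is close to that of 10 mg IV (2.395) and about 313.2/2.471 = 127 times below that of 1000 mg IV. ECGs at and far above SC peak levels are therefore already captured within 12 h in the IV cohorts. This stands too and keeps the point minor.

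A longer window has a cost. It would mix triplicate means through 96 h with noisier single readings from Day 32. That is a reason to label the result and read it against placebo. It does not make a pre-peak window informative for SC dosing.

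Two outputs come near to filling the gap without doing so. The vital-sign categories cover pulse rate, which is not ECG heart rate. Protocol 9.6.1 asks for a count of uncorrected QT at or above 500 msec, which is a threshold on the absolute value and not a maximum increase.

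**Conclusion.** The point holds in limited form. One descriptive table uses a window that misses peak exposure for the one SC cohort, and for ECG heart rate and uncorrected QT it is the only per-subject maximum summary.

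The window ends at about 13–21% of SC peak concentration. This rests on first-order absorption and either the projected parameters or the preliminary Table 1 values. Observed Tmax also depends on the sampling visits: Day 15 is nominally 14 × 24 = 336 h, and the neighbouring samples are at Day 8 and Day 32. That is why a range is given. The figure falls to about 3% only if Tmax is 1080 h.

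A reader might infer that the SC row reflects almost no drug. That fits the first hour or two but not the end of the window. The projected share absorbed by 12 h, 1 − exp(−0.18 × 0.5) = 8.6%, is a fraction of dose and should not be read as a fraction of peak concentration. Nor would any choice of window show the ECG at the median SC Tmax, because none is scheduled between 96 h and Day 32.

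For the IV cohorts the window is reasonable at the median (1.76–3 h in healthy subjects, 2 h in CRSwNP), although individual CRSwNP values range up to 170 h.

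**What to change.** In SAP 8.1.9, for Cohort 7, active and placebo alike, take the maximum increase over all planned and unplanned post-dose ECGs. This is the counting rule the section already uses for its categories. Alternatively, add an all-post-dose column for every cohort. That option also shows the other Part 1 placebo subjects over the same period, which helps because Cohort 7 planned only 2. Keep 0–12 h as a labelled column for the IV cohorts.

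Add a footnote that no Part 1 ECG is scheduled between 96 h and Day 32, so the median SC Tmax is not sampled.

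The cost is a sentence of SAP text, a footnote and one table column, with no new data. The downside is that a maximum over up to 15 scheduled readings instead of 4, mixing triplicate means with single ECGs, is larger by chance. Its size depends on within-subject ECG variability, which the documents do not give, so the column should be read only against placebo over the same period.
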